7.5.4. Vital Signs

- Vital signs will be measured in semi-supine position after 5 minutes rest and will include temperature, systolic and diastolic blood pressure and pulse rate and respiratory rate.

7.5.5. Electrocardiogram (ECG)

- Single 12-lead ECGs will be obtained at each time point during the study using an ECG machine that automatically calculates the heart rate (HR) and measures PR, QRS, QT, and QTc intervals. Refer to Section 5.5 for QTc withdrawal criteria and additional QTc readings that may be necessary.
- Continuous cardiac telemetry will be performed. Full disclosures will be reviewed in detail and the review maintained as part of the subject's source documents

7.5.6. Clinical Safety Laboratory Assessments

This study will use local laboratory except for liver event. All protocol required laboratory assessments, as defined in [Table 6](#), must be conducted in accordance with Protocol Time and Events Schedule. Reference ranges for all safety parameters will be provided by the local laboratory responsible for the assessments.

If additional non-protocol specified laboratory assessments are performed at the institution's local laboratory and result in a change in subject management or are considered clinically significant by the investigator (e.g., SAE or AE or dose modification) the results must be recorded in the CRF.

Refer to the SRM for appropriate processing and handling of samples to avoid duplicate and/or additional blood draws.

Haematology, clinical chemistry, urinalysis and additional parameters to be tested are listed in [Table 6](#).

Table 6 Protocol Required Safety Laboratory Assessments

Laboratory Assessments	Parameters			
Haematology	Platelet Count	Red blood cells (RBC) Indices:	White Blood Cells (WBC) count with Differential :	
	RBC Count	MCV	Neutrophils	
	Hemoglobin	MCH	Lymphocytes	
	Hematocrit		Monocytes	
			Eosinophils	
			Basophils	
Clinical Chemistry ¹	Blood urea nitrogen (BUN/UREA)	Potassium	AST (Serum glutamic-oxaloacetic transaminase (SGOT))	Total and direct bilirubin
	Creatinine	Sodium	ALT (Serum glutamic pyruvic transaminase (SGPT))	Total Protein
	Glucose	Calcium	Alkaline phosphatase	Albumin
Routine Urinalysis ²	
 • Specific gravity • pH, glucose, protein, blood and ketones • Microscopic examination (if blood or protein is abnormal) 			

NOTES :
 
 1. Details of Liver Chemistry Stopping Criteria and Required Actions and Follow-Up Assessments after liver stopping or monitoring event are given in Section 5.5.2 and Appendix 2 2. Local urine testing will be standard for the protocol unless serum testing is required by local regulation or ethics committee. 				

All laboratory tests with values that are considered clinically significantly abnormal during participation in the study or within 4 days after the last dose of study treatment should be repeated until the values return to normal or baseline. If such values do not return to normal within a period judged reasonable by the investigator, the etiology should be identified and the sponsor notified.

8. DATA MANAGEMENT

- Management of clinical data will be performed in accordance with applicable GSK standards and data cleaning procedures to ensure the integrity of the data, e.g., removing errors and inconsistencies in the data.
- Adverse events and concomitant medications terms will be coded using MedDRA (Medical Dictionary for Regulatory Activities) and an internal validated medication dictionary, GSK Drug.
- CRFs (including queries and audit trails) will be retained by GSK, and copies will be sent to the investigator to maintain as the investigator copy. Subject initials will not be collected or transmitted to GSK according to GSK policy.
- For this study subject data will be collected using GSK defined case report forms and combined with data provided from other sources in a validated data system.

9. STATISTICAL CONSIDERATIONS AND DATA ANALYSES

9.1. Hypotheses

The study is designed to provide an estimated mean treatment difference between active drug groups and placebo group in primary efficacy endpoint, change from baseline of daily rTNSS over the first 2 weeks treatment period. This is a descriptive study and no formal inference is planned.

The primary comparisons of interest between treatment groups are:

FF 55 µg vs Placebo

FF 110 µg vs Placebo

As a supportive comparison, the pooled active drug groups (low and high-dose) will be compared with placebo.

Although no formal inference is planned, statistical models will be used to estimate mean differences between interest comparisons. Point estimates and corresponding 95% confidence intervals (CIs) will be presented for each treatment comparison. All the results from analyses model are descriptive and no statistical conclusion will be claimed.

9.2. Sample Size Considerations

9.2.1. Sample Size Assumptions

This is a descriptive study and no formal inference is planned. The planned sample size is mainly based on the feasibility and regulatory requirement (100 evaluable subjects per arm).

The study is planned for a total of 360 randomized subjects (120 subjects per each treatment group). It is assumed that 17% subjects will not be evaluable for the primary analysis. Therefore, the total of 360 randomized subjects should provide 100 evaluable subjects per arm. Among 100 evaluable subjects per arm, at least 50 subjects are ≥ 2 to ≤ 6 years old.

With a common standard deviation (SD) of 2.6 for the primary endpoint, based on previous global FF pediatric studies [FFR30008, FFR100010], a sample size of 100 subjects per treatment group ensures that the half-width of 95% CI of the treatment difference between active drug and placebo is no larger than 0.725 for the age groups ≥ 2 to ≤ 12 years old and a sample size of 50 subjects per treatment group ensures the half-width of 95% CI no larger than 1.032.

It is assumed that the treatment difference between active drug and placebo in change from baseline of daily rTNSS over the first two weeks treatment period for FF 110 μg is 0.5 and FF 55 μg is 0.3 based on the pooled analysis of previous global FF pediatric studies [FFR30008, FFR100010]. With 100 subjects per treatment group for ≥ 2 to ≤ 12 years old and 50 subjects per group for ≥ 2 to ≤ 6 years old, the probabilities of observing a positive trend, i.e. at least one active drug is numerically superior to placebo, is calculated by means of simulation. As shown in below table, the probability of observing a positive trend in subjects aged ≥ 2 to ≤ 12 years and subjects aged ≥ 2 to ≤ 6 years is 95% and 90% respectively. The probability of observing a positive trend in both age groups is 88%.

Subjects aged ≥ 2 to ≤ 12 years old (100 subjects per arm)	Subjects aged ≥ 2 to ≤ 6 years old (50 subjects per arm)	In both age groups
95%	90%	88%

9.2.2. Sample Size Sensitivity

The assumption of a standard deviation of 2.6 for primary endpoint, change from baseline in diary rTNSS over the first two weeks treatment period, is based on the estimated from previous studies. However, the actual standard deviation in this study may deviate from 2.6. The following table presents the precision of the two sided 95% CI based on different standard deviations for a sample size of 100 subjects per treatment group aged ≥ 2 to ≤ 12 years and 50 subjects per treatment group aged ≥ 2 to ≤ 6

Common standard deviation	Distance from mean to limit (1/2 of the width of the 95% confidence interval)	
	Subjects aged ≥ 2 to ≤ 12 years old (100 subjects per arm)	Subjects aged ≥ 2 to ≤ 6 years old (50 subjects per arm)
2.4	0.669	0.953
2.5	0.697	0.992
2.6	0.725	1.032
2.7	0.753	1.072
2.8	0.781	1.111

If the assumed the treatment difference between active drugs and placebo is not exactly 0.3 for low dose and 0.5 for high dose, the probabilities of observing a positive trend calculated in Section 9.2.1 will not hold. Based on historical data, it is assumed that the treatment difference between high dose and placebo follows a normal distribution $N(0.5, 0.5)$, and the treatment difference between low dose and placebo follows a normal distribution $N(0.3, 0.5)$. The common SD is assumed to be 2.6. Based on the above assumptions, the probability of observing a positive trend is re-calculated as following

In ≥ 2 to ≤ 12 years old subjects (100 subjects per arm)	In ≥ 2 to ≤ 6 years old subjects (50 subjects per arm)	In both age groups
91%	88%	85%

9.2.3. Sample Size Re-estimation or Adjustment

Due to the uncertainties about standard deviation, the pooled SD will be monitored in blinded way. The pooled SD will be adjusted according to the assumed treatment effect. If the adjusted SD is much larger than 2.6, team will determine whether to increase sample size based on feasibility and the re-calculated probability of observing a positive trend.

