3. OBJECTIVE(S) AND ENDPOINT(S)

Objectives	Endpoints
Primary	

 To establish the efficacy of FFNS 55 µg and 110 µg QD versus vehicle placebo nasal spray over a period of 2 weeks in pediatric subjects (ages 2 to 12 years) with AR 	
 Mean change from baseline over the first 2 weeks treatment period in daily, reflective total nasal symptom scores (rTNSS) in subjects aged 2 to 12 years
Secondary	

 To investigate the safety of FFNS 55 µg and 110 µg QD versus vehicle placebo nasal spray over a period of 4 weeks in pediatric subjects (ages 2 to 12 years) with AR 	
Secondary efficacy endpoints
 
 Overall evaluation of response to therapy (evaluated on a 7-point categorical scale) after the first 2 weeks treatment (day15) Mean change from baseline of intranasal finding score by anterior rhinoscopy at the first 2 weeks (day 15) Mean change from baseline over the first 2 weeks treatment period in the daily, reflective total ocular symptoms score (rTOSS) Rescue loratadine use (mean rescue-free days) over the first 2 weeks treatment period Mean change from baseline over the 4 weeks treatment period in daily rTNSS Overall evaluation of response to therapy after 4 weeks treatment period (day 29) The mean change from baseline of intranasal finding score by anterior rhinoscopy at the end of treatment(day 29) Mean change from baseline over the 4 weeks treatment period in the daily rTOSS Rescue loratadine use (mean rescue-free days) over the entire 4 weeks treatment period 
Safety endpoints
 
 Frequency and type of clinical adverse events Results of clinical laboratory tests (Hematology and chemistry) Results of physical and nasal examination Vital signs (temperature, systolic and diastolic blood pressures, pulse rate, respiratory rate)

[figure not shown]

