9.3. Data Analysis Considerations

9.3.1. Analysis Populations

The intent-to-treat (ITT) population is defined as all randomized subjects who received at least one dose of study drug. Subjects will be assessed according to the treatment they are randomised to. This population will be the primary analysis population for efficacy analysis. Additional output(s) may be provided if subjects are mistakenly treated but not randomized to support safety tables.

The Subset ITT population (2 to 6 years old) is defined as a subset of ITT population comprising subjects aged ≥ 2 to ≤ 6 years old.

The per protocol (PP) population is defined as all randomized subjects in ITT population who do not have any full protocol deviations. This population will be used for supportive analysis of the primary efficacy endpoint only. These detailed criteria of full protocol

deviations will be defined in the Reporting and Analysis Plan (RAP). The PP population will not be analyzed if this population comprises more than 95% or less than 50% of the ITT population.

All the summary and analysis will be performed for both ITT population and Subset ITT population (2 to 6 years old). Both the ITT, Subset ITT and PP populations will be determined prior to unblinding of the study.

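### Should the blinded sample-size review in Protocol 9.2.3 use the chance that both doses beat placebo, rather than at least one?

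*Protocol*

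**What the plan says.** - **The review rule (Protocol 9.2.3).** The pooled SD is monitored blind and adjusted for the assumed treatment effect. Only if the adjusted value is much larger than 2.6 does the next step follow: the "team will determine whether to increase sample size based on feasibility and the re-calculated probability of observing a positive trend".
- **The event (Protocol 9.2.1).** It is defined openly: "the probabilities of observing a positive trend, i.e. at least one active drug is numerically superior to placebo, is calculated by means of simulation". The printed chances are 95% for ages 2 to 12 (100 per arm), 90% for ages 2 to 6 (50 per arm) and 88% for both populations together. Section 9.2.2 repeats the exercise with uncertain effects and prints 91%, 88% and 85%.
- **The basis of the size (Protocol 9.2.1).** The planned number rests chiefly on feasibility and on a regulatory figure of 100 evaluable children per arm.
- **The objective and comparisons.** Section 3 opens the primary objective with "To establish the efficacy of FFNS 55" µg and goes on to 110 µg. Section 9.1 introduces its list with "The primary comparisons of interest between treatment groups are" and gives 55 µg versus placebo and 110 µg versus placebo as two lines, with a pooled comparison as support. It adds: "Point estimates and corresponding 95% confidence intervals (CIs) will be presented for each treatment comparison". No formal inference is planned and no statistical conclusion is to be claimed. SAP 2.4 carries the same two comparisons.
- **Populations (Protocol 9.3.1).** "All the summary and analysis will be performed for both ITT population and Subset ITT population". Section 9.4.1 calls the younger subset supportive.

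**The concern.** The objective names both doses, yet the probability consulted before adding children is satisfied when either one is ahead. That event is easy to meet. With an inert drug and equal arms, placebo has the best mean of the three one time in three, so at least one active arm still looks better 67% of the time.

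The event also reacts slowly to the SD. At 100 per arm it falls only from 95.3% at SD 2.6 to 94.3% at SD 2.8 and 89.1% at SD 4.0. The chance that both doses look better falls from 75.3% to 72.9% and 62.3%.

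In a descriptive trial the direction and size of each dose's estimate are the result. If the protocol's assumed effects are exactly right, there is still a 25% chance that at least one dose shows no advantage in ages 2 to 12. There is a 42% chance that at least one of the four reported comparisons (two doses, two populations) points the wrong way. The fear is that a reassuring 94% would hide this from the team, and that readers would take 95/90/88% as covering both doses.

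**Working it through.** **Inputs.** Section 9.2.1 starts "With a common standard deviation (SD) of 2.6 for the primary endpoint" and assumes differences of 0.5 (110 µg) and 0.3 (55 µg), with 100 evaluable per arm, or 50 in ages 2 to 6, and 17% not evaluable. Allocation is 1:1:1, so both differences share one placebo arm.

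**Model.** The two estimated differences are bivariate normal. Each has variance 2·SD²/n and their covariance is SD²/n, so the correlation is 0.5.

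**Step 1: reproduce the printed figures.**

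- n = 100: SE = 2.6·√(2/100) = 0.368. P(110 µg ahead) = Φ(0.5/0.368) = 0.913. P(55 µg ahead) = Φ(0.3/0.368) = 0.793. P(both ahead) = 0.753. At least one = 0.913 + 0.793 − 0.753 = 0.953 (printed 95%).
- n = 50: SE = 2.6·√(2/50) = 0.520. The same steps give 0.832, 0.718 and 0.646, and at least one = 0.903 (printed 90%).
- Both populations, simulated with the 50 younger children inside the 100: 0.883 (printed 88%).
- Uncertain effects: for 110 µg, 9.2.2 says "it is assumed that the treatment difference between high dose and placebo follows a normal distribution" with mean 0.5, and the low dose is treated likewise with mean 0.3. Reading the second parameter, 0.5, as an SD and the doses as independent gives 91.5%, 88.6% and 85.8% (printed 91%, 88%, 85%). A correlation of 0.1 between the doses gives 90.8% and 88.0% for the first two.

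The protocol's figures are right for the event it defines.

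**Step 2: the alternative event.** Both doses ahead has probability 75.3% (ages 2 to 12), 64.6% (ages 2 to 6) and 58.0% (both populations). With uncertain effects it is 56.0% and 53.1% in the first two. These are also correct, but they answer a different question.

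**Step 3: does the choice change the review's answer?** For fixed effects and a fixed correlation of 0.5, each probability depends on SD and n only through SD/√n. To return either one to its planned value after the SD rises, n must grow by (new SD/2.6)²:

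- SD 2.8: 100 × (2.8/2.6)² = 115.98, so 116 per arm. At least one is again 95.3% and both is again 75.3%.
- SD 4.0 (an assumption, outside the protocol's table): 100 × (4.0/2.6)² = 236.7, so 237 per arm under either quantity.

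The two differ only against an absolute level. At an assumed 80%, at least one is met with large room. Both doses is not met at the planned SD of 2.6 and n of 100 (75.3%). It would need 134 evaluable per arm at SD 2.6 or 156 at SD 2.8. Randomized numbers are then 3 × ⌈134/0.83⌉ = 3 × 162 = 486 and 3 × ⌈156/0.83⌉ = 3 × 188 = 564, against 360.

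**Step 4: precision per comparison.** The half-width is t × SE: 1.972 × 0.3677 = 0.725 at 100 per arm and 1.984 × 0.520 = 1.032 at 50. Both are printed in 9.2.1. Section 9.2.2 tabulates them for SDs from 2.4 to 2.8. They apply to each dose versus placebo.

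**The case for a change.** The best case for acting is this. Section 9.2.3 does not tell the team to restore the planned value. It sets no minimum and does not define how large an SD counts as much larger, so the team may simply look at the figure and ask whether it is acceptable. On that reading 94% reassures where 73% might not. The regulatory 100 per arm explains the starting size, not the rule for exceeding it. Nor does either document say that one dose is enough.

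Part of this stands. The chances for 55 µg alone (79.3%), for 110 µg alone (91.3%) and for both doses (75.3%) are not printed, and a hasty reader could over-read the 95%. The rule leaves room for judgement.

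None of it makes the criterion wrong. Naming two doses in an objective does not turn them into a joint success condition, and 9.1 treats them as separate estimates. A level of 80% for both doses would be a quarrel with the original 100 per arm, which was not chosen on this probability, rather than with the review rule. The SD 2.8 example is weak: it is about 8% above 2.6 (2.8/2.6 = 1.077), lies inside the protocol's own sensitivity table, and may never reach the probability step. The proposed quantity itself moves only from 75.3% to 72.9% there. The 67% for an inert drug would matter if the event were a test of success, but it is a planning summary and no claim is tied to it. Two of the four comparisons behind the 42% belong to a subset labelled supportive.

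**Conclusion.** The concern does not hold. The printed probabilities are correct for a clearly stated event, and no passage requires both doses to be ahead of placebo. The gap between 95% and 75% is the difference between two legitimate planning summaries, on which statisticians may reasonably differ. When the planned chance is restored after a larger SD, both lead to the same number (116 per arm at SD 2.8). They separate only against a level the documents do not contain, and adopting 80% for both doses would mean 486 to 564 randomized children for numerical direction alone in a descriptive trial. Printing the per-dose chances would be a courtesy to the reader. It would alter no estimate, interval or conclusion.

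This rests on a common SD, normal means, equal arms sharing one placebo group, and the protocol's effects of 0.5 and 0.3. For 9.2.2 it also rests on reading the second parameter of the normal distribution as an SD.

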2. SUMMARY OF KEY PROTOCOL INFORMATION

2.1. Changes to the Protocol Defined Statistical Analysis Plan

There were no changes or deviations to the originally planned statistical analysis specified in the protocol (Dated: 15-JAN-2016).

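### Does the blinded sample-size review in Protocol 9.2.3 need a numeric SD trigger and a target probability?

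*Protocol*

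**What the plan says.** Protocol 9.2.3 states that "the pooled SD will be monitored in blinded way" and that the value is adjusted for the assumed treatment effect. The condition for acting is "If the adjusted SD is much larger than 2.6". In that case the "team will determine whether to increase sample size based on feasibility and the re-calculated probability of observing a positive trend".

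The probability in question is defined in 9.2.1 as that of "observing a positive trend, i.e. at least one active drug is numerically superior to placebo". Two versions are printed, each for ages 2 to 12, ages 2 to 6, and both together:

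- 9.2.1, fixed effects of 0.5 (110 µg) and 0.3 (55 µg): 95%, 90%, 88%.
- 9.2.2, effects drawn from N(0.5, 0.5) and N(0.3, 0.5): 91%, 88%, 85%. It is introduced with the remark that, if the effects differ from those assumed, "the probabilities of observing a positive trend calculated in Section 9.2.1 will not hold", and then "Based on the above assumptions, the probability of observing a positive trend is re-calculated as following".

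On what fixes N, 9.2.1 says: "The planned sample size is mainly based on the feasibility and regulatory requirement", meaning 100 evaluable per arm from 120 randomised. The SAP has no section on re-estimation. Its Section 2.1 says "There were no changes or deviations to the originally planned statistical analysis specified in the protocol", which concerns the analysis and not the sample size.

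**The concern.** A re-estimation provision normally says when the look happens, what value triggers action and what quantity the new N must restore. Section 9.2.3 names a criterion but none of these. It also does not say which of the two printed calculations is to be re-run, and 9.2.2 uses the same term, re-calculated, for its own version.

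Read literally, one team might leave N alone and another might enlarge a placebo-controlled trial in children, both from the same blinded SD and both within the protocol. For example, at an assumed SD of 3.0, a target of 95% for ages 2 to 12 with fixed effects needs 128 evaluable per arm (28% more than 100), while a target of 90% needs only 64, so no increase.

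**Working it through.** **Inputs.** From 9.2.1: SD 2.6; n = 100 evaluable per arm, 50 of them aged 2 to 6; effects 0.5 and 0.3; 17% not evaluable. From 9.2.2: the random-effect distributions and SDs up to 2.8. SD 3.0 is an assumed value, not in the plan. The model is normal without covariates and with a shared placebo arm. In 9.2.2 the second 0.5 is read as an SD (τ) and the two dose effects as independent.

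**Formula.** P(trend) = 1 − Φ₂(0, 0), where Φ₂ is the bivariate normal CDF with means 0.3 and 0.5, variances 2·SD²/n + τ² and covariance SD²/n. τ = 0 gives the 9.2.1 version and τ = 0.5 the 9.2.2 version. The half-width is t(0.975, 2n−2)·SD·√(2/n).

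**Step 1: the plan's own figures.** At SD 2.6:

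| Version | Ages 2–12 | Ages 2–6 | Both (simulated) | Printed |
|---|---|---|---|---|
| 9.2.1 | 95.3% | 90.3% | 88.3% | 95 / 90 / 88% |
| 9.2.2 | 91.5% | 88.6% | 85.8% | 91 / 88 / 85% |

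The first row matches and the second is within one point. The half-widths of 0.725 (n = 100) and 1.032 (n = 50) reproduce.

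**Step 2: what a larger SD does if N stays at 100 per arm (ages 2–12).**

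| SD | P(trend), 9.2.1 | P(trend), 9.2.2 | Half-width |
|---|---|---|---|
| 2.6 | 95.3% | 91.5% | 0.725 |
| 2.8 | 94.3% | 91.0% | 0.781 |
| 3.0 | 93.4% | 90.5% | 0.837 |

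The 9.2.1 figure drops below 90% only above SD 3.76.

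**Step 3: does the choice of calculation matter?** In both versions SD and n enter only through SD²/n. Returning either version to its own planned value therefore needs the same n = 100·(SD/2.6)²:

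- SD 2.8: 100 × (2.8/2.6)² = 115.98, so 116 per arm.
- SD 3.0: 100 × (3.0/2.6)² = 133.14, so 134 per arm.

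A direct search gives 116 and 134 for both versions. Restoring the planned half-width gives 116 and 133. At 17% loss, 116/0.83 = 139.8, so 140 randomised per arm (420 in all); 134/0.83 = 161.4, so 162 per arm (486 in all).

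**Step 4: where the wider spread comes from.**

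- The 128 at SD 3.0 aims at the rounded 95% rather than 95.3%. It also needs an SD above any in the plan's table; at SD 2.8 the same target gives 111.
- The corresponding 9.2.2 figures, 101 at SD 2.8 and 115 at SD 3.0, aim at the rounded 91% rather than 91.5%.
- The 64 aims at 90% for ages 2 to 12, but the plan prints 90% only for ages 2 to 6. It also lies below the required 100 evaluable per arm.

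**Step 5: the blinded adjustment.** Arm effects of 0, 0.3 and 0.5 at 1:1:1 have variance 0.042, so a within-arm SD of 2.6 appears as √(6.76 + 0.042) = 2.608. The missing adjustment formula makes no practical difference.

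**The case for a change.** The best case for a change is that the sponsor chose to write a re-estimation provision and named its criterion. Feasibility can cap an increase but cannot say what increase was wanted. One or two sentences giving a trigger (say 2.8, the top of the 9.2.2 table) and a target (the planned probability) would let a decision to add children, or not, be traced to a written rule without committing the sponsor to anything.

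It stands that 9.2.3 gives no trigger, target or review time, and that the SAP does not fill them in. The benefit claimed for the added sentences is weaker:

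- The number of subjects at the review would still have to be chosen, and the team would still decide subject to feasibility. Two teams could still differ.
- A trigger of 2.8 is itself a judgement. On a single look with a true SD of 2.6 it would fire by chance 13% of the time with 100 subjects and 3% with 300. The 9.2.1 figure slips below 95% already at SD 2.66.
- The review is blinded and there is no hypothesis test, so the discretion cannot inflate a type I error or steer N by the observed effect. The actual confidence intervals are reported whatever N is reached.

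**Conclusion.** No change is needed. Section 9.2.3 is short on detail, but it describes a blinded decision limited by feasibility, in a descriptive study whose N rests mainly on feasibility and the 100-per-arm requirement. If the SD proves larger and N is kept, the 9.2.1 probability for ages 2 to 12 loses about 1 point at SD 2.8 and about 2 points at SD 3.0, and the half-width widens by 0.056 and 0.112. No estimate or conclusion becomes wrong.

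A team that does want to act has a natural target in the plan's own figures: restore the planned probability or half-width. That leads to 116 per arm at SD 2.8 and 133 or 134 at SD 3.0, and both printed calculations agree. Which one is re-run is therefore not a real ambiguity.

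This rests on a normal model without covariates, the effects assumed in 9.2.1, the SD reading of N(0.5, 0.5) with independent dose effects, and half of each arm aged 2 to 6. SD 3.0 is illustrative.
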